## 7.2. SECONDARY ENDPOINTS

### - Reduction of crisis intensity and duration, as well as medication consumption.

Crisis intensity (mild, moderate, severe), duration in hour, and the number of treatments taken will be collected in the migraine agenda (annex 1) filled by the patient. These variables will be compared between the month before music therapy initiation and the 3rd month of treatment.

### - Reduction of functional and emotional impact.

Questionnaires HAD and HIT (annex 2) will be completed with the investigator during the inclusion visit before initiation of music therapy, and at Month 3 visit.

- Questionnaire HAD to evaluate emotional impact (national reference HAS « chronic pain: recognize chronic pain syndrome, evaluate it and guide the patient »)
- Questionnaire HIT to evaluate functional impact (guideline of the International Headache society)

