## 4. STUDY DESIGN

### 4.1. METHODS

Monocentric, prospective before-after study.

It comprises of only one group of patients and all of them will receive the intervention.

The study will measure and compare migraine frequency during the month before inclusion with migraine frequency 3 months after the inclusion.

- **Entry in the study:** based on proposition of algologist doctor involved in the patient care and after patient receives information and signs inform consent.

- **Inclusion period:** the month before the initiation of music session will serve as reference period. Patient will fill migraine diary, complete questionnaires on functional and emotional impact used usually in the department.

The following endpoints will be evaluated:

- migraine severity (number of days with migraine, duration, intensity, treatment)
- questionnaire HAD to evaluate emotional impact
- questionnaire HIT to evaluate functional impact

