## 7.6. INCLUSION VISIT

During this visit, a complete information on objectives and course of the study is provided to the patient. Informed consent is collected by the algologist investigator of the study.

Diagnosis questionnaire, and HAD and HIT questionnaires HAD et HIT are completed with the investigator. Migraine agenda to be filled during the next 3 months is provided to the patient.

A training to *Music care*, music therapy software, is realized by the study responsible. Details on methodology, objectives of the technique, as well as the optimal conditions of use are given to the patient. During this visit, the first music session is done at the hospital under medical control. A questionnaire is filled in order to have a better knowledge of migraine patient about music preferences likely to bring him to relaxation.

A secure account is created to allow patients to have a free internet access and use *Music care* during the study.

At the end of this visit, the patient should be able to use at home by himself the software and to realize music therapy sessions using *Music care*.

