## 7.8. END OF STUDY VISIT

This final visit corresponds to the follow-up visit at Month 3. Final data collection on migraine agenda will be realized as well as HAD and HIT questionnaires filled with the algologist.

---

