#### MIGRAINE DIARY

Please fill in the migraine calendar daily and specify each day:

Migraine

Headache intensity: mild, moderate or severe

Duration in hours of headache

Migraine treatments used

Date	Migraine/tension headache	Intensity	Duration	Treatments
D1				
D2				
D3				
D4				
D5				
D6				
D7				
D8				
D9				
D10				
D11				
D12				
D13				
D14				
D15				
D16				
D17				
D18				
D19				
D20				
D21				
D22				
D23				
D24				
D25				
D26				
D27				
D28				
D29				
D30				
D31				

## 16.2. APPENDIX 2

Please fill the 2 questionnaires below:

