### HAD QUESTIONNAIRE

D	A		D	A	
		I feel tense or 'wound up':			I feel as if I am slowed down:
	3	Most of the time	3		Nearly all the time
	2	A lot of the time	2		Very often
	1	From time to time, occasionally	1		Sometimes
	0	Not at all	0		Not at all
		I still enjoy the things I used to enjoy:			I get a sort of frightened feeling like 'butterflies' in the stomach:
0		Definitely as much		0	Not at all
1		Not quite so much		1	Occasionally
2		Only a little		2	Quite Often
3		Hardly at all		3	Very Often
		I get a sort of frightened feeling as if something awful is about to happen:			I have lost interest in my appearance:
	3	Very definitely and quite badly	3		Definitely
	2	Yes, but not too badly	2		I don't take as much care as I should
	1	A little, but it doesn't worry me	1		I may not take quite as much care
	0	Not at all	0		I take just as much care as ever
		I can laugh and see the funny side of things:			I feel restless as I have to be on the move:
0		As much as I always could		3	Very much indeed
1		Not quite so much now		2	Quite a lot
2		Definitely not so much now		1	Not very much
3		Not at all		0	Not at all
		Worrying thoughts go through my mind:			I look forward with enjoyment to things:
	3	A great deal of the time	0		As much as I ever did
	2	A lot of the time	1		Rather less than I used to
	1	From time to time, but not too often	2		Definitely less than I used to
	0	Only occasionally	3		Hardly at all
		I feel cheerful:			I get sudden feelings of panic:
3		Not at all		3	Very often indeed
2		Not often		2	Quite often
1		Sometimes		1	Not very often
0		Most of the time		0	Not at all
		I can sit at ease and feel relaxed:			I can enjoy a good book or radio or TV program:
	0	Definitely	0		Often
	1	Usually	1		Sometimes
	2	Not Often	2		Not often
	3	Not at all	3		Very seldom

Please check you have answered all the questions

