**HIT-6™**  
(VERSION 1.1)

This questionnaire was designed to help you describe and communicate the way you feel and what you cannot do because of headaches.

To complete, please circle one answer for each question.

1	When you have headaches, how often is the pain severe?	Never	Rarely	Sometimes	Very Often	Always
2	How often do headaches limit your ability to do usual daily activities including household work, work, school, or social activities?	Never	Rarely	Sometimes	Very Often	Always
3	When you have a headache, how often do you wish you could lie down?	Never	Rarely	Sometimes	Very Often	Always
4	In the past 4 weeks, how often have you felt too tired to do work or daily activities because of your headaches?	Never	Rarely	Sometimes	Very Often	Always
5	In the past 4 weeks, how often have you felt fed up or irritated because of your headaches?	Never	Rarely	Sometimes	Very Often	Always
6	In the past 4 weeks, how often did headaches limit your ability to concentrate on work or daily activities?	Never	Rarely	Sometimes	Very Often	Always

To score, add points for answers in each column.

Please share your HIT-6 results with your doctor.

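### HAD and HIT-6 are printed for the patient to fill in but are to be completed with an unblinded study doctor, an avoidable risk of response bias at Month 3.

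*Protocol*

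**What the plan says.** **How the questionnaires are completed.** Protocol 7.2 states that HAD and HIT-6 "will be completed with the investigator during the inclusion visit before initiation of music therapy, and at Month 3 visit", and SAP 3.2 has the same sentence. Protocol 7.6 says of Day 0 that the "HAD and HIT questionnaires HAD et HIT are completed with the investigator". Protocol 7.8 has, at Month 3, "HAD and HIT questionnaires filled with the algologist".

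**What the forms say.** Appendix 2 opens with "Please fill the 2 questionnaires below". The HAD items are in the first person, and the form ends with "Please check you have answered all the questions". HIT-6 instructs: "To complete, please circle one answer for each question". It then asks the respondent to share the result with the doctor.

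**Text pointing to patient completion.** Protocol 4.1 says that in the reference period the patient will "complete questionnaires on functional and emotional impact used usually in the department", with no mention of a doctor.

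**Design.** Protocol 4.1: "It comprises of only one group of patients and all of them will receive the intervention". There is no control group and no independent assessor. HAD and HIT-6 are analysed before versus after with the Wilcoxon signed rank test (Protocol 9.2, SAP 5.2).

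**The concern.** HAD and HIT-6 are subjective scores, and they are the plan's only measures of the emotional and functional objectives. A patient who answers beside a member of the team that offered the therapy may give a more favourable picture than one who answers alone. At Day 0 there is not yet any therapy to be polite about. At Month 3 there have been three months of it, and under Protocol 7.4 and 7.7 that same visit counts the sessions done and evaluates motivation. A courtesy effect could therefore enter at one end of the comparison only and look like improvement.

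The documents give no reason for involving the doctor. The diary variables, by contrast, are filled in by the patient (Protocol 7.2).

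**Working it through.** The plan states no figure on this point, so the check is a comparison of the texts followed by a short argument about what cancels.

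**1. Mode of completion, side by side**

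| Place | Who completes HAD and HIT-6 |
|---|---|
| Protocol 4.1 (reference period) | the patient; no doctor mentioned |
| Protocol 7.2 and SAP 3.2 | with the investigator, both visits |
| Protocol 7.6 (Day 0) | with the investigator |
| Protocol 7.8 (Month 3) | with the algologist |
| Appendix 2 (the forms) | instructions addressed to the patient |

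The visit and endpoint sections consistently involve a doctor. The forms and 4.1 do not.

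**2. Who that doctor is.** Protocol 4.1 has the study proposed by the algologist in charge of the patient. Protocol 7.6 has the study responsible give the training. Protocol 4.1 gives the monthly visits, Month 3 included, to an intern of general medicine, and 7.1 has the intern check the diary at each monthly visit. Protocol 7.4 and 7.7 give the follow-up visits to the investigator, and 7.8 names the algologist for the final forms. Whether these roles fall to one person cannot be settled from the text. Whoever it is belongs to the study team and knows the treatment.

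**3. What cancels.** Write a patient's score as Day 0 = T0 + m + error and Month 3 = T3 + m + s + error. Here T is the true state, m is any effect of the doctor's presence common to both visits, and s is a shift in answering that exists only at Month 3. The paired difference is (T3 − T0) + s + error. The constant m drops out; s stays. With one group, no comparison in the analysis estimates s.

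**4. What private completion can change.** Part of s would exist even if the patient answered alone, for example from expectation. The fix removes only the extra part caused by the doctor's presence.

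**5. Illustration only.** The documents give no SD for HAD or HIT-6 and no estimate of s. Assume no true change, normal paired differences, n = 20 and the exact two-sided 5% Wilcoxon signed rank test (20,000 simulated trials). Let d be the favourable Month 3 shift in SDs of the paired difference.

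| Assumed d | Significant and favourable |
|---|---|
| 0 | 2.5% |
| 0.1 | 6.2% |
| 0.2 | 12.8% |
| 0.3 | 23.8% |
| 0.5 | 53.6% |

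Each rate is per score and ignores ties in integer scores. The table shows how the test responds to a given shift. It is not evidence that any shift of this size occurs.

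**The case against.** **The mode is the same at both visits.** This is correct and disposes of any constant effect. It does not dispose of a shift specific to Month 3.

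**Completing a form *with* a doctor may mean only in the doctor's presence.** This stands. Protocol 4.1 and the forms allow that reading, so one should not infer that the doctor interviews the patient and records the answers. Presence is a weaker influence than an interview, but it is still not private completion.

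**One might infer that the doctor who proposed and taught the therapy also sits beside the patient at Month 3.** The documents do not establish this, because the sections disagree on who runs that visit. The concern needs only an unblinded member of the team.

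**One might read the table above as the trial's false-positive rate.** It is not. The shifts are chosen inputs with no anchor in the documents. The relevant quantity, the excess over private completion, may be small.

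**The real limitation is the missing control group.** This also stands. Improvement in HAD or HIT-6 could not be attributed to music with confidence even if the forms were completed privately. HIT-6 itself invites the patient to show the result to the doctor, so a wish to please is reduced at most.

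**Conclusion.** The point holds as a minor, inexpensive improvement. The plan has two patient-reported questionnaires completed with an unblinded study doctor, against the way the forms are written and without a stated reason. This creates an avoidable risk of response bias in two secondary endpoints. The documents do not show that bias will occur, and its size cannot be estimated from them.

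The conclusion rests on one assumption: that some patients would answer more favourably in a doctor's presence after three months of therapy than they would alone, and that this exceeds any such tendency at Day 0. If the tendency is equal at both visits, it cancels and nothing is lost. The diary-based primary endpoint and the sample size are unaffected.

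**What to change.** In Protocol 7.2, 7.6 and 7.8 and in SAP 3.2, replace completion with the doctor by the following:

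- The patient completes HAD and HIT-6 alone.
- At Day 0 this is done after written consent and before Music Care training. Protocol 7.6 collects consent at that same visit, so the forms must not simply be handed out before the consultation.
- At Month 3 it is done before the patient discusses results with the study doctor.
- Staff check only that every item is answered and note on the form any help given with reading.

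Changing the protocol alone would leave the SAP in conflict with it. Make 4.1 consistent with the new wording, and reconcile 4.1 and 7.1 with 7.4, 7.7 and 7.8 on who conducts the Month 3 visit.

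Use one mode per patient. A patient whose Day 0 forms were completed with a doctor should not switch at Month 3, since the mode effect would then no longer cancel. If data have already been collected, report the mode as a limitation.

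The cost is protocol and SAP wording, with no added visit, instrument or patient, and some doctor time is saved. The downside is that a few patients may need help or leave items blank. Expectation effects and regression to the mean remain and should still be stated when the results are reported.

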## 7.3. ESTIMATED TIMELINES OF THE RESEARCH

- Start of inclusion: November 2018
- Duration of retrospective observational period: 1 month
- Duration of patient participation: 3 months
- Total duration of the study: 4 months

## 7.4. SUMMARY TABLE OF PATIENT FOLLOW-UP

	Screening visit M-1	Inclusion visit Day 0	Month 1 visit	Month 2 visit	Month 3 visit
Patient information	✓				
Training on agenda migraine completion	✓				
Training on Music care use		✓			
Inform consent collection		✓			
Diagnosis questionnaire		✓			
Check on number of music sessions			✓	✓	✓
Check on migraine agenda completion		✓	✓	✓	✓
Questionnaires HAD et HIT		✓			✓

Screening visit will be done by the medical responsible of the study, PH algologist. Inclusion and follow-up visits will be also done by the investigator.

All the visits will be performed at Chronic Pain Department of CHU-GHSR site of Saint-Louis.

Follow-up visits will be done monthly after inclusion visit with a window of +/- 1 week.

## 7.5. SCREENING VISIT

Screening visit will be managed by the algologist responsible of the study. It will be done between 4 months and 1 month before inclusion visit.

### 7.5.1. PATIENT INFORMATION

During screening visit and before any evaluation or data collection, the investigator will inform the patient of the study and propose him to participate. The following points will be described:

- Objectives and design of the study,
- Data collection and processing, access rights.

Migraine agenda (usually used by the team) will be provided to the patient in order to complete the 1-month observational period.

During this visit, inclusion and exclusion criteria will be verified. If the patient agrees to participate, oral consent will be provided.

## 7.6. INCLUSION VISIT

During this visit, a complete information on objectives and course of the study is provided to the patient. Informed consent is collected by the algologist investigator of the study.

Diagnosis questionnaire, and HAD and HIT questionnaires HAD et HIT are completed with the investigator. Migraine agenda to be filled during the next 3 months is provided to the patient.

A training to *Music care*, music therapy software, is realized by the study responsible. Details on methodology, objectives of the technique, as well as the optimal conditions of use are given to the patient. During this visit, the first music session is done at the hospital under medical control. A questionnaire is filled in order to have a better knowledge of migraine patient about music preferences likely to bring him to relaxation.

A secure account is created to allow patients to have a free internet access and use *Music care* during the study.

At the end of this visit, the patient should be able to use at home by himself the software and to realize music therapy sessions using *Music care*.

## 7.7. FOLLOW-UP VISITS

Follow-up visits will be monthly done by the investigator, at Month 1, Month 2 and Month 3 after inclusion. During these visits, checks will be done regarding agenda migraine completion, patient motivation will be evaluated, and the number of music sessions done will be collected.

Impressions and feeling of the patient regarding music sessions will be collected.

## 7.8. END OF STUDY VISIT

This final visit corresponds to the follow-up visit at Month 3. Final data collection on migraine agenda will be realized as well as HAD and HIT questionnaires filled with the algologist.

---

## 7.9. SPECIAL MODALITIES OF CARE

Music therapy use does not require special modalities of care.

## 8. GESTION OF SERIOUS ADVERSE EVENTS

No procedure for serious adverse events is imposed by the research. Nevertheless, declaration of serious adverse events to the regional center of pharmacovigilance is mandatory for all doctor and health professional.

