STANDARD CARE NATURE EVALUATED IN THIS RESEARCH	Sessions of music therapy self-directed by the patient at home, using Music Care software via an internet connexion.
EVALUATION CRITERIA	
Primary evaluation criterion Reduction of migraine frequency of 50% after 3 months.
 
Secondary evaluation criteria Reduction of migraine intensity and duration, as well as acute treatment administration. Reduction of the emotional and functional impact.

PLANNED SAMPLE SIZE	20 patients
PLANNED CENTERS	1 centre: Chronic Pain Department of CHU-GHSR site of Saint-Louis
DURATION OF THE RESEARCH	
 
- Duration of inclusion period: 1 month
 
- Duration of patient participation: 3 months
 
- Total duration of the study: 4 months
 

STATISTICAL ANALYSIS	
Analysis of the primary endpoint The mean number of migraine crises per month before and after music therapy will be compared using the Wilcoxon Paired Test.
 
Analysis of secondary endpoints Quantitative variables before and after music therapy will be analysed using Wilcoxon Paired Test. Qualitative variables will be analyzed using McNemar Chi test.

EXPECTED RESULTS	
To propose a new therapeutic and non-drug approach in episodic migraine prophylaxis.
 
To improve the relationship between medical team and patients.
 
To reduce the treatment consumption.

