#### - **Music therapy session implementation**

Each patient will be asked to follow 1 to 2 sessions per day for 3 months, to be done at home, using *music care* software via internet connexion.

They will complete the migraine diary during the 3 months of the study.

They will have a visit at the Chronic Pain Department every month, so at Month 1, 2 and 3, realised by an intern of general medicine.

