## **11. QUALITY CONTROL**

### **11.1. INFORMATION FOR DATA COLLECTION**

All information required by the protocol shall be recorded on the observation books and an explanation shall be provided for each missing data. Data should be collected as they are obtained and transcribed into these books in a neat and legible manner.

Incorrect data found on the observation books will be clearly crossed out and the new data will be copied, next to the crossed-out information, accompanied by initials, the date and possibly justification by the person who is directing and monitoring the research or the authorized person who made the correction.

Data are collected on a paper CRF.

The data to be collected directly in the CRF will be:

- age, sex
- migraine diagnosis according to International Headache Society criteria
- number of days with headache per month
- duration and intensity of crises
- headache treatment medication per month
- HAD and HIT

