**- where applicable, for a period of 30 years following the completion of the research**

- A copy of the signed informed consent of the participants
- Documents related to serious adverse events

All these documents are under the responsibility of the project manager for the statutory archiving period.

No movement or destruction shall be carried out without the approval of the manager. At the end of the statutory archiving period, the manager will be consulted for destruction. All data, documents and reports will be subject to audit or inspection.

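### The plan describes no systematic recording or analysis of adverse events or of stopping because of the music, and names no one in the study to receive serious-event documents

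*Protocol*

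**What the plan says.** Protocol section 8 consists of two sentences. The first is "No procedure for serious adverse events is imposed by the research". The second recalls that "declaration of serious adverse events to the regional center of pharmacovigilance is mandatory for all doctor and health professional". The synopsis describes the intervention as "Sessions of music therapy self-directed by the patient at home, using Music Care software via an internet connexion", and its first expected result is "To propose a new therapeutic and non-drug approach in episodic migraine prophylaxis".

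Section 11.1 introduces its list with "The data to be collected directly in the CRF will be". The list covers age and sex, diagnosis, headache days, duration and intensity of attacks, headache medication, and HAD and HIT. At Months 1, 2 and 3, section 7.7 adds checks of the diary, of motivation and of the session count, and asks how the patient felt about the sessions.

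Section 13 includes "Documents related to serious adverse events" among the papers that the project manager keeps for 30 years, under a heading that applies only if such papers exist.

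The SAP has no safety endpoint and no safety table. Its single population (section 4) requires one music session and enough diary data to evaluate the primary endpoint at Month 3.

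**The concern.** The study is meant to support a new prophylactic approach, and a prophylactic is judged on tolerability as well as benefit. The protocol itself foresees a tolerability question: section 6.1 notes that attacks often bring phonophobia and advises sessions outside attacks, while leaving patients free to listen during one. Nothing in the plan says where an unwanted reaction to a session would be written down, who in the study would be told of a serious one, or how either would be reported. A report that mentions no harm could then mean that none occurred or that none was asked about, and a reader could not tell which.

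**Working it through.** The plan states no figure on this point, so the check is mainly a reading of the places where an adverse event could enter the data.

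1. **Is an event asked for?** The visit table (7.4) lists information, training, consent, diagnosis, session count, diary check and questionnaires. The source-data list (10.2) names the CRF, the questionnaires and the diary. The CRF list (11.1) is as given above. None has an adverse-event item. Section 8 speaks only of serious events, so the gap for non-serious events rests on these three lists.

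2. **Does the general recording rule in 11.1 fill the gap?** It requires everything the protocol asks for to be recorded and every missing value to be explained. That covers session counts and patients' impressions, although neither is in the list. It does not cover adverse events, because no section asks for them. A patient who stops the sessions but keeps the diary has no missing diary value to explain, so the reason for stopping need not be written anywhere.

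3. **Would the efficacy data show harm?** In part.
   - Month 3: headache frequency, intensity, duration and medication, with HAD and HIT, are compared with baseline, so marked worsening would be visible.
   - Months 1 and 2: the diary is kept, but the final evaluation (4.1) uses the third month, and HAD and HIT are taken only at Day 0 and Month 3. Earlier worsening that has passed by Month 3 enters no planned comparison.
   - Any month: a reaction tied to a session that is not a headache has no field.

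4. **Who is counted?** Someone who gives up both the sessions and the diary fails the SAP section 4 definition and leaves the only analysis set. Such patients may be the most informative about tolerability.

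5. **Where would a serious-event document go?** Section 8 names an outside body. Section 13 foresees an archive held by the project manager. No section links the two.

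**What 20 patients could show if events were recorded** (n = 20, Protocol 9.1):
- Upper limit after 0 of 20, one-sided 95%: 1 − 0.05^(1/20) = 13.9%.
- Upper limit of the two-sided exact 95% interval: 1 − 0.025^(1/20) = 16.8%.
- Chance of seeing at least one affected patient, 1 − (1 − p)^20: 18% if the true rate p is 1%, 64% if 5%, 88% if 10%. These three rates are illustrative and are not in the documents.

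**The case against.** The case on the other side is substantial. The protocol presents the study as research on routine care (12.1) and says that music therapy needs no special modalities (7.9), so section 8 looks deliberate. Patients take migraine medication, so a pharmacovigilance route is not irrelevant to them. The first session is supervised at the hospital, three department visits follow, and at each one patients say how they found the sessions. With 20 patients, even perfect recording says little about uncommon harm.

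Most of this stands, and it rules out several stronger readings that a reader might be tempted by:
- *That harms never reach the data, not even worsened headache.* Worsened headache is what the diary measures, and impressions and session counts are collected monthly.
- *That sections 8 and 13 flatly contradict each other, or that the administrator must archive papers it never receives.* The archive heading is conditional, and section 13 names the project manager. The protocol does not say that this is the same party as the administrator. This is a loose end.
- *That having no procedure breaches the rules.* Whether the routine-care frame permits it cannot be settled from these documents.
- *That the disagreement over who holds the monthly visits proves the gap.* Section 4.1 has them "realised by an intern of general medicine", while section 7.7 says "Follow-up visits will be monthly done by the investigator". That needs reconciling on its own account, but it neither causes nor shows the gap described here.

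None of this supplies a defined event record, a recorded reason for stopping, or an analysis that retains patients who stop.

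**Conclusion.** The point holds in a limited form. The documents describe no systematic recording, analysis or onward reporting within the study of adverse events or of stopping because of the music. What stays out of sight is specific: events linked to sessions, worsening confined to Months 1 and 2, reasons for stopping, and patients who drop out of the analysis set. Month 3 worsening is not among them.

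The consequence is for what can be said about tolerability. The primary endpoint, its test and the sample size are untouched. In numbers, the plan forgoes a bound of 13.9% or 16.8% after 0 of 20, which is weak but reportable. Those figures assume that all 20 patients are asked and that patients are independent. The textual conclusion assumes that no separate safety form exists outside the two documents. This is a cheap improvement and not a flaw that threatens the main result.

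**What to change.** - **Protocol section 8 and 11.1:** at Day 0, after the supervised session, and at the Month 1, 2 and 3 visits, ask one open question on undesirable effects. Add one CRF line for the event, its date, whether it was serious, its relation to a session, and any stopping of sessions with the reason.
- **Sections 8, 11.1 and 13:** reconcile them by naming who in the study receives serious-event documents, so that the project manager's archive can be kept when such documents exist. The declaration duty that section 8 recalls can stay as it is.
- **SAP:** add one table of events and of stops, with exact 95% confidence intervals. Its denominator should be everyone who had one or more sessions, whatever the state of their diary, and not the section 4 population.

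The cost is a few minutes per visit, one CRF line, one table and a small reporting duty for the centre. No visit is added, and neither the sample size nor the primary analysis changes. The change concerns what is recorded and reported, and sets no rule for patient care.
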